	Weeks 1-8	Weeks 9-12	Weeks 13-16	Weeks 17-20	Weeks 21-24	Weeks 25-28	Weeks 29-32			
iAmHealthy Intervention	8 weekly sessions	1 session	1 session	1 session	1 session	1 session	1 session			
	11 hours of homework help via remote technology									

in the area of pediatric obesity treatment, children who receive at least 25 contact hours over a 6-8 month period are significantly more likely to be successful than children who receive fewer hours.²²

B. Sample Criteria

- 1. Sample Size:
 - a. About 144 parent/child pairs (8 or more parent/child pairs at 18 schools). Approximately 175 parent/child pairs will be consented to have 144 children go on to enrollment.
- 1. Inclusion/Exclusion Criteria:
 - a. Inclusion Criteria:
 - i. Family lives in a rural area (city and/or county population <20,000)
 - ii. Child BMI >85th and <99th percentile
 - iii. Child in 2nd thru 4th grade
 - iv. Both child and parent speak English
 - v. Family is available at times intervention is offered
 - b. Exclusion Criteria
 - i. Child has physical limitation or receives and injury which significantly limits physical activity
 - ii. Child has significant medical issue known to the school (i.e. cancer)
 - iii. Child and/or parents have a significant developmental delay or cognitive impairment that is known to the school

- iv. Child has a sibling already enrolled in the program
- v. Family moves to a non-participating school

C. Enrollment, Consent, and Procedures.

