Following completion of all baseline measures (which will take one hour; see Measures below), iAmHealthy families will receive their technology devices via postal service and will be scheduled for a 30-minute phone orientation session to all technology. Intervention components will then be implemented for iAmHealthy or newsletter. Weight and height measurements will be taken at each child's school at the start of the intervention and monthly throughout the intervention period for both parents and children by onsite trained staff. Parents or children may have their weight taken at a local hospital or clinic if a medical specialty scale is needed, such as a wheelchair scale or a high-capacity scale. In the event schools are closed (ie. COVID-19 outbreak), parents will be trained on how to obtain height and weight at home. Digital scales and tape measures will be sent to the families, and each family will measure the height and weight during a video call via Zoom app with an iAmHealthy team member to ensure measurement accuracy. At the completion of the intervention (8 months later), the second one-hour measures collection will take place. Sixteen months following the end of the intervention, the third one-hour measures collection will take place (20-month follow-up).

Families from the intervention/control study will be paid proportionally for completion of measures as is required by our local IRB (\$80 at baseline, 8 months, and 20 months, plus \$100 for monthly heights and weights over 10 time points). Participants who wear the activity monitors for at least 7 days will receive an extra \$20 at baseline, 8 months, and 20 months. Altogether, families may receive up to \$400. A payment timeline for participants is attached below:

	Start of Study	1 Month	2 Month	3 Month	4 Month	5 Month	6 Month	7 Month	8 Month	20 Month	Total for Study Completion
Online Surveys	\$80								\$80	\$80	

Height & Weight	\$10	\$10	\$10	\$10	\$10	\$10	\$10	\$10	\$10	\$10	
Activity Monitors	\$20								\$20	\$20	
Total	\$110	\$10	\$10	\$10	\$10	\$10	\$10	\$10	\$110	\$110	\$400

In case of activity monitor malfunction, we would like to be able to offer an additional \$20 for the participant to wear the device again. Thus, a participant could earn over \$400 if they are asked to wear the monitor a 2nd time.

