In case parents or children need to be weighed on a medical specialty scale at another location (local hospital or clinic), we would like to be able to offer an additional \$10 each timepoint for the participant's time in collecting the measurement at another location. If this is the case, a participant could earn over \$400.

In the event schools are closed (ie. COVID-19 outbreak), participants will receive an additional \$10 for each completed study measure, up to an additional \$100. If this is the case, a participant could earn over \$400. Participants will be informed of this change over the phone, and not asked to come into the school to be reconsented.

The onsite school representative will be paid for their services to the study outside of normal school hours/duties (\$30/hr, up to \$2000 per completed site). If the onsite school representative leaves employment with the school, they will be replaced by another suitable school employee selected by the principal. Schools will also be allowed to retain the scales and stadiometers provided by the study, although participants will be required to return all technology equipment, including the iPads.

D. Data Collection

Measures will be completed through REDCap, a secure, web-based application designed exclusively to support data capture for research studies, just prior to the start of the intervention (**baseline**), immediately following the 8-month intervention (**8 months**), and 16 months after the end of the intervention (**20 months**), with the exception of parent and child weight, which will be taken at these time points as well as monthly throughout the 8 month intervention time period. See Table 6 for the Measures Timeline.

Primary Measures

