- 2. Child Body Mass Index z score (BMIz) and Parent Body Mass Index (BMI). To calculate child BMIzand parent BMI we will use standard formulas/equations. Height and weight will be assessed by fully trained onsite school representatives on standardized, calibrated equipment provided by the study. All staff will be trained in standard research anthropometric measurement protocol, including calibration techniques. Standing height will be assessed in

Table 6. Measures timeline.			
Primary Outcome Measures	Baseline	8 months	24 months
24 hour food recall (child)	Х	Х	Х
Physical Activity Monitors (child)	Х	Х	Х
Child BMIz/ Parent BMI ¹	Х	X	Х
R each			
Participation	Х	Х	
Structured Interviews with Non- participants		Х	
E fficacy			
HRQOL (parent, child)	Х	Х	Х
Parent Distress (parent)	Х	Х	Х
Peer Victimization (child)	X	Х	X
Child Depression (child)	Х	Х	х
Satisfaction (parent, child)		х	
Stigma (parent, child)		Х	
A doption			
Assess Representativeness of Participating Schools	Х		
I mplementation			
Attendance/Participation		Х	
Cost		Х	
Group Process		Х	
M aintenance			
Structured Interviews With Participating Schools		Х	
Other Measures			
Demographics (parent)	Х		
Food Insecurity	Х		
Post Questionnaire (parent)		Х	
Technology Feasibility (parent)	Х	Х	
$^{1}\mbox{Child BMIZ/Parent BMI will be taken monthly throughout}$	the 8 month into	ervention period	

triplicate via a Harpenden Holtain stadiometer, Model 603 (Holtain, Crymych, UK). Weight will be measured in triplicate on a portable SECA digital scale (SECA, Hamburg, Germany) after the participant has been asked to void. Parents and children will be measured with light clothing and no shoes.

Other Measures

1. *Demographics*. This questionnaire will ask about age, race, ethnicity, income, free/reduced lunch status, and parental education. We will also assess for the availability of home computers, high-speed internet access, tablets, smartphones, or other technology already present in the home that could be utilized for secure videoconference

- connections in future studies.

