- 7. **Peer Victimization.** Peer victimization will be assessed via the Schwartz Peer Victimization Scale which assesses the frequency of overt and relational forms of peer victimization among children. For each item, children are asked to rate how often they experience a specific form of peer victimization (e.g., gossip, hitting/pushing). Higher scores suggest higher levels of victimization.
- 8. *Child Depression*. Child depressive symptoms will be assessed via the Children's Depression Inventory–Short Form (CDI-SF). The CDI-SF⁴³ screens for the presence of depressive symptomatology over the past 2 weeks. Higher scores indicate higher symptom severity. This measure asks about a child's thoughts of suicide. Study staff will view the responses to this measure within 3 days of the measure being completed. If a child indicates they want to commit suicide on the measure, the PI who is a licensed child psychologist will be notified. The PI then review the child's other relevant measures and contact the parent to decide if a referral to local support centers is necessary.
- 9. *Parent and Child Satisfaction*. Our existing parent measure is 18 items and will be slightly modified for the current study to add two questions focused on the delivery method of the intervention (iPad, newsletter). The child satisfaction measure was developed specifically for the current study and will shadow the parent satisfaction items. The questions will be read to the child by a research staff member without the parent present in order that parents do not influence child responses. Specific to technology, we will also administer the 12-item Parent-Reported Satisfaction Measure which previous research has shown to be reliable and valid, 45 assessing three technology-related satisfaction domains: technical, comfort with technology and perceived privacy, and access. We will also randomly select a subset of participants to do a structured phone interview about parent satisfaction.

Stigma. Stigma specific to participation will be measured by asking the parent: "Has your child been the victim of any stigma as a result of participation in this intervention program?" or the child: "Have people made fun of you because you were in iAmHealthy?" as is common in treatment related stigma measurement.

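### The suicide-item procedure allows up to 3 days before staff see a child's answer and sets no time limit for reaching the parent

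*Combined protocol and SAP*

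**What the plan says.** Item 8 (Child Depression) under Other Measures in II.D Data Collection notes that the CDI-SF asks about suicidal thoughts and sets out three steps.

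- Viewing: "Study staff will view the responses to this measure within 3 days of the measure being completed".
- Escalation: "If a child indicates they want to commit suicide on the measure, the PI who is a licensed child psychologist will be notified".
- Action: "The PI then review the child's other relevant measures and contact the parent to decide if a referral to local support centers is necessary".

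Only the first step carries a time limit. On how the data are captured, the opening of II.D says: "Measures will be completed through REDCap, a secure, web-based application". Table 6 schedules the child depression measure at baseline, 8 months and the final follow-up. The inclusion criteria in II.B describe the population as "Child in 2nd thru 4th grade".

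**The concern.** The protocol itself treats this answer as serious enough to need a licensed child psychologist and a conversation with the parent. Having made that judgement, it should also limit how long the process may take. As written, the study can hold a young child's statement of wanting to commit suicide for up to 3 days before any staff member reads it, without breaching the protocol. It can then take an unstated further time to reach the parent, with whom the PI decides on referral. The measure is given three times, so the exposure recurs. What is at stake is the protection of individual children. No estimate or test in the analysis plan depends on it.

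**Working it through.** There is no computed figure in the plan to reproduce. The check is a reading of each step for its time limit, followed by simple arithmetic on the limits.

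**Steps and limits (II.D, item 8)**

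| Step | Time limit in the supplied text |
|---|---|
| Child's answer to staff viewing | 3 days |
| Staff viewing to PI notification | none stated |
| PI notification, review of other measures, parent contact | none stated |

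Longest permitted time from answer to parent contact = 3 days + unstated + unstated. The text therefore sets no upper bound.

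**Whether another section closes the gap.** The rest of the supplied text was searched for an alert, a same-day check, a shorter limit or a safety-monitoring procedure covering this item. None was found. II.D names REDCap as the capture system but describes no automatic alert. The payment table in II.C lists online surveys at baseline, 8 months and 20 months. Item 9 of Other Measures has research staff read questions to the child, but only for the satisfaction measure. It cannot be presumed that someone sees the CDI-SF answer as it is given.

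**Size of the viewing window**

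- Calendar days: 3 × 24 = 72 hours.
- Working days (the text does not say which): a form completed on a Friday could wait until Wednesday, which is 5 calendar days, or 5 × 24 = 120 hours.
- A 24-hour viewing rule, compared with the calendar-day reading: 72 − 24 = 48 hours off the ceiling.

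These are differences between maximum times, not between expected times.

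**What an overall limit leaves for the later steps, if staff take the full 24 hours to view**

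- Overall limit 48 hours: 48 − 24 = 24 hours for PI review and parent contact.
- Overall limit 24 hours: 24 − 24 = 0 hours, so a 24-hour total does not work with a 24-hour viewing rule.

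**Workload.** About 144 children (II.B) × 3 time points (Table 6) = about 432 forms if every child completes every assessment, spread over the 5-year study mentioned in II.A. One item per form needs checking.

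The documents give no rate for the trigger answer, so the number of children affected cannot be estimated.

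**The case against.** The strongest reply is that the plan already handles this risk. It recognises the suicide item, sets a viewing window, escalates to a qualified clinician and requires parent contact and a referral decision. Three days is a ceiling, and same-day viewing is fully compatible with it. Nothing in the documents makes 24 hours right and 3 days wrong. This stands in part: the rule permits a delay and does not impose one, and the particular target is a matter of clinical judgement. It does not answer the missing limits on the two later steps.

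A second reply is that unseen by study staff does not mean unseen by any adult. The documents do not say who is with the child during the CDI-SF, so a reader might infer that the parent can learn of the answer only through staff. The text does not support that inference, nor does it establish that an adult is present.

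A third is that a faster procedure may exist elsewhere. Consent pages were removed and a separate safety plan is possible. A reader might infer that the trial has no faster safeguard at all; the documents show only that none appears in the supplied text.

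Finally, the remedy is not free of conditions. Whether the study's REDCap set-up supports alerts is not stated, and an alert sent at submission does not ensure that the PI reads it promptly. Nor do the documents say that the CDI-SF is always completed at a supervised sitting on predictable days. II.C describes planned collections ("the second one-hour measures collection will take place"), but forms completed online on evenings or weekends would need out-of-hours checking. These points stand and are reflected in the fix.

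**Conclusion.** The point holds as one about timing. Item 8 permits an answer indicating a wish to commit suicide to go unseen by study staff for up to 3 days, and the supplied text puts no limit on PI notification or parent contact. The interval from answer to parent contact is therefore unbounded. The 72-hour figure assumes calendar days.

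Two stronger readings should be resisted. The plan does not lack a safeguard: the pathway names a qualified role and ends in parent contact and a referral decision. Nor does the rule require staff to wait. The finding is confined to the supplied text and carries no estimate of how many children would be affected. It is a cheap improvement that the sponsor should make.

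**What to change.** Amend item 8 as follows.

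1. If the REDCap set-up supports it, send an automatic alert to the PI when the trigger answer is submitted, and keep staff viewing as a backup.
2. If it does not, require staff to view the suicide item within 24 hours of completion instead of 3 days.
3. State one overall limit in hours from submission to parent contact, set by the PI. For example, 48 hours leaves 24 hours after a 24-hour viewing for PI review and parent contact.

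Stating the limits in hours also removes the ambiguity between calendar and working days. If a faster procedure already exists in another document, it need only be written into item 8.

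The cost is an IRB amendment, the alert set-up, possibly more PI reviews, and some weekend or evening checking if forms are completed out of hours. No new assessor, visit or measure is needed.

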The primary aim of this study is to assess the effectiveness of rural pediatric obesity treatment delivered virtually to family homes (iAmHealthy) compared to an active attention control group (control). This is a cluster randomized design, with schools being assigned to condition (iAmHealthy or control) and the 8 parent/child pairs at each school being assigned to the same condition. Having children and families from the same school participate in the same mHealth group allows us to target the unique environmental characteristics that are both barriers to and facilitators of success in iAmHealthy.

II. Research Plan and Design

A. Design and Intervention.

The intervention is a cluster randomized design as groups will be randomized by school. Schools will be contacted via a flyer sent to all 550 rural elementary schools in the state of Kansas. Schools will contact researchers via a toll-free number and given detailed instructions on how to complete the required human subjects training and earn Institutional Review Board approval. Recruited schools will be stratified by two key variables (school size, percent free/reduced lunch) and then assigned to one of the intervention groups, such that all children/families who sign up at each elementary school will be assigned by school as a single group to either iAmHealthy or control (i.e., randomization occurs at the school level, not at the individual level). Any subsequent schools will be waitlisted for participation the next year.

Once 6 schools are randomized, they will be sent research grade scales and stadiometers and trained by research staff in all measurement and intervention procedures. At this time school representativeness will be analyzed each year, and if schools are not representative on either of the key metrics, schools recruited the following year will be oversampled in order that schools reach a representative sample by the end of the 5-year study.

The iAmHealthy family-based intervention provides behavioral, nutrition, and physical activity topics (see Table 4 and Appendix A). The intervention has an 8-week intensive weekly intervention phase followed by a 6-month period of

Table 4. iAmHealthy Standard Int	Rurally Tailored Topics	
Goal Setting & Sticker Charts	Reading Food Labels	Decreased focus on fast food
Stop Light Diet Parent Health Behavior Changes	Energy Balance Use of Privileges	Increased focus on eating at social gatherings

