Some outcomes will be analyzed using the multilevel model described above with a baseline covariate. These outcomes include Efficacy outcomes for parent and child reports of HRQOL, parent distress, child depression, and child peer victimization. A second set of outcomes involve tests of treatment condition differences where a baseline covariate is not available. These outcomes will be analyzed similarly with a multilevel model, however there will not be a level-1 covariate for the outcome at baseline. Outcomes to be analyzed in this manner include: parent and child satisfaction within Efficacy as well as attendance, participation, and cost from Implementation. The stigma outcome within Efficacy will be analyzed by comparing the proportions reporting child stigmatization between treatment conditions. This will be done for both child and parent report. A third set of outcomes will be examined descriptively. These outcomes include participation from Reach as well as descriptions of the barriers obtained in the qualitative analysis, school-level demographics from Adoption, engagement from Implementation, the number of schools retaining intervention components and summaries of factors related to maintenance from Maintenance. Participant demographics, reported food insecurities, and technological feasibility will also be examined descriptively.

Missing Data. While attrition and incomplete data may be unavoidable, the deleterious effects missing data may have on our results can be mitigated through a combination of careful data collection and thoughtful analysis. Full information maximum likelihood estimation which uses all available data to build a multidimensional likelihood function for each highest-level unit (schools) will be used for the multilevel models. For variables brought into the likelihood function, any missing cases are assumed missing at random, which means random only after conditioning on model predictors and the observed outcomes. Reasons for student departure (e.g., dropout versus changing schools) can be tracked and included as model predictors to help reduce the bias that might otherwise be created.

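### The only child stigma item names the experimental condition but is compared between conditions, so the two child-reported proportions may not measure the same thing

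*Combined protocol and SAP*

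**What the plan says.** The Stigma paragraph in section II.D (Other Measures, after item 9) sets out to measure stigma tied to participation, with one question per informant. The child is asked "Have people made fun of you because you were in iAmHealthy". The parent is asked "Has your child been the victim of any stigma as a result of participation in this intervention program". No separate newsletter wording is given for either. Table 6 lists stigma, for parent and child, under Efficacy at 8 months only.

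Section II.E gives the analysis: "The stigma outcome within Efficacy will be analyzed by comparing the proportions reporting child stigmatization between treatment conditions". It adds: "This will be done for both child and parent report". It names no test or significance level for this outcome.

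On the meaning of the name, section I.B describes "schools being assigned to condition (iAmHealthy or control" as the two alternatives, and section II.C contrasts iAmHealthy with newsletter when it describes implementation. The same word is also the study title, forms the protocol ID, and in section II.C describes the staff who supervise remote height and weight measurement.

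**The concern.** A between-arm comparison of proportions needs a question that means the same in both arms. The child item attributes the teasing to membership of something called iAmHealthy. For a child in an iAmHealthy school that is unambiguous. For a newsletter child it can mean a programme the child was not in, so that a child teased for taking part would answer no. It can also mean the study, and such a child would then answer yes.

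The true newsletter rate need not be zero. Children in both arms are selected on BMI percentile (section II.B), and the school height and weight measurements in section II.C are not limited to one arm. There are therefore occasions in both arms for a child to be noticed and teased.

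At stake is the trial's only measure of stigma attributed to participation. If the item under-records in the newsletter arm, an apparent excess in iAmHealthy could come from the wording alone. A null result would not be reassuring either, because under-recording in one arm changes the contrast by an unknown amount. Stigma has no baseline value, so adjustment cannot repair this.

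**Working it through.** **No figure to reproduce.** The documents give no expected stigma rate, effect size or power for this outcome. The core of the check is a comparison of texts, and the arithmetic only shows how much could depend on the ambiguity.

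**Texts side by side.**
- Item (II.D, Stigma): one child wording, which names iAmHealthy.
- Analysis (II.E): child-reported proportions are compared between conditions.
- Label (I.B, II.C): iAmHealthy is the experimental condition, against control or newsletter.
- Competing use (title, protocol ID, II.C): iAmHealthy is also the study and its team.
- Contrast within II.D: item 9 adapts the parent satisfaction measure to both delivery methods, iPad and newsletter. Nothing similar is stated for stigma.

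**Illustration: inputs.**
- Children per arm: n = 72. Section II.B gives 8 × 18 = 144 pairs. The equal split, 144 / 2 = 72, is an assumption, because no allocation ratio is stated.
- p: true rate of teasing for taking part, equal in both arms. Assumed, with a range of 5% to 20%.
- q: share of teased newsletter children who can answer yes to the item as worded. Unknown, range 0 to 1.
- Test: two-sided Fisher at 0.05, also an assumption. Clustering by school is ignored.

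**Expected apparent difference with no real one:** p − pq = p(1 − q). At p = 10% this is 10 percentage points for q = 0, 5 points for q = 0.5, and 0 for q = 1.

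**Significance threshold when the newsletter arm records none.** For x of 72 against 0 of 72, the two-sided p-value is 2 × C(72, x) / C(144, x):
- x = 5: 0.058
- x = 6: 0.028
- x = 7: 0.013

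Six yes answers in the iAmHealthy arm would be enough.

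**Chance of a spurious significant difference.** Let A ~ Bin(72, p) and B ~ Bin(72, pq). Sum P(A = a) × P(B = b) over all pairs (a, b) with Fisher p < 0.05. For q = 0 this reduces to P(A ≥ 6).

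| True rate p | q = 0 | q = 0.25 | q = 0.5 | q = 1 |
|---|---|---|---|---|
| 5% | 15.1% | 7.2% | 3.4% | 1.4% |
| 10% | 73.8% | 31.6% | 12.0% | 2.6% |
| 15% | 96.8% | 55.6% | 21.8% | 3.0% |
| 20% | 99.8% | 73.8% | 31.6% | 3.2% |

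The last column is a wording that works in both arms.

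**The opposite error.** Suppose the true rates were 10% in iAmHealthy and 20% in newsletter, with q = 0.5. The expected recorded proportions would be 10% and 20% × 0.5 = 10%, so a real difference would vanish.

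**The case against.** The strongest reply is that iAmHealthy is also the name of the study. On that reading a newsletter child is asked about being in the study, which is what a neutral wording would ask, and q is close to 1. The description of the measure as specific to participation fits this. The protocol does not reproduce the questionnaires, so an adapted newsletter form may exist. This stands as far as it goes: the newsletter answer is ambiguous, not fixed. It does not rescue the comparison, because the plan states no adapted form and nothing in the planned data shows which reading each child took.

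A reader might go further than the documents allow in four ways.
- **That the control proportion is bound to be zero.** The use of the name for the study and its team rules that out as a certainty. The q = 0 column is the extreme case.
- **That the parent item has the same fault.** It refers to an intervention programme and names no arm, and item 9 of section II.D treats the newsletter as a delivery method of the intervention. A newsletter parent can answer about what the family received.
- **That stigma is the trial's only measure of teasing.** Sizing Me Up has a teasing and marginalization scale, and the Schwartz scale measures peer victimization. Both are collected at baseline and follow-up, and section II.E models HRQOL and peer victimization with a baseline covariate. Only attribution to participation is unique to the stigma item.
- **That the 12-item technology satisfaction measure shares the problem.** No section says that newsletter families complete it or that it is tested between arms.

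**Conclusion.** The concern holds for the child report. The plan puts to both arms a question worded with the experimental arm's label, then compares the answers between arms. The two proportions cannot be relied on to measure the same thing, and neither a difference nor its absence has a clean interpretation.

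The size cannot be fixed from the documents. At an assumed true rate of 10% in both arms, the chance of a spurious significant result runs from about 74% (q = 0) through about 12% (q = 0.5) to about 3% with wording that works in both arms. That last figure stays within about 1% to 3% for rates of 5% to 20%. All of this rests on assumed rates, equal arms of 72, a Fisher test at 0.05 and no allowance for clustering.

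The outcome is not primary and a usable parent report sits beside it, so no primary conclusion is affected. The change is still worth making: it is cheap, and the outcome bears on possible harm from taking part.

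**What to change.** Use one arm-neutral child question in both arms, for example asking whether people made fun of the child *because you took part in this study*, and make that item the one compared between conditions. If a newsletter version of the form is already in use, state its wording in section II.D.

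Do not pool answers already collected under the present wording with answers to the new item. Report them separately, as a descriptive proportion in the iAmHealthy arm only. The parent item can stay as it is.

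This takes one reworded item and one added sentence in section II.E. The downside is that fewer answers are available for the between-arm comparison of child-reported stigma, because those collected before the change no longer contribute to it.
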